7.8.1. Adverse Events

Summary tables and listings will be provided for all reported treatment emergent adverse events (TEAEs), defined as AEs that start on or after the first day of any study drug that is administered and within 30 days of the last administration of any study drug. Missing and partially missing AE start dates will be imputed according to the specification described in Appendix A. The reported AE will be coded using MedDRA (version 16.1 for Phase 1; version 21.1 or higher for Phase 2a). AEs severity grading scales in Phase 1 are based on the NCI CTCAE version 4.03. For AEs in Phase 2a, AE severity grades are mixture of grading scales of the NCI-CTCAE version 4.03 and the NCI CTCAE version 5. No imputation of AE grades will be performed. AE with missing CTCAE grade will only be summarized in the all-grade column.

The causal relationship between the occurrence of an AE and each treatment will be assessed by the investigator. For summary of related AEs, causality assessment by the investigator per eCRF will be mapped based on Table 2. If the assessment of the relationship of an AE to study treatment is missing, the AE is assumed to be related to the study treatment in the table summary. No imputation will be done in the AE listings.

Table 2. Causality Mapping of AEs

Relationship to Study Drug per Investigator	Summary of AEs
Unrelated	Not related
Unlikely	Not related
Possible	Related
Probable	Related

TEAEs will be summarized based on the number and percentage of subjects experiencing AEs. When summarizing TEAEs by MedDRA system organ class (SOC) and preferred term (PT), a subject reporting the same AE more than once will be counted only once when calculating the incidence 1) within a given SOC, and 2) within a given SOC-PT combination. Similarly, a same AE will be counted only once within a PT when summarizing by PT only. In both situations, the maximum CTCAE toxicity grade and the strongest causal relationship to the study drug for such events will be used.

Tabular summaries of the following will be provided:

- TEAEs by PT
- TEAEs by SOC, PT
- TEAEs by SOC, PT, and maximum severity grade
- Grade 3 or higher TEAEs by PT
- Grade 3 or higher TEAEs by SOC, PT
- Grade 3 or higher TEAEs by SOC, PT and maximum severity grade
- Cerdulatinib-related TEAEs by PT
- Cerdulatinib-related TEAEs by SOC, PT
- Cerdulatinib-related TEAEs by SOC, PT, and maximum severity grade
- Rituximab-related TEAEs by PT (Cohort 2 only)
- Rituximab-related TEAEs by SOC, PT (Cohort 2 only)
- Rituximab-related TEAEs by SOC, PT, and maximum severity grade (Cohort 2 only)
- Serious TEAEs by PT
- Serious TEAEs by SOC, PT
- TEAEs leading to cerdulatinib discontinuation by PT
- TEAEs leading to cerdulatinib discontinuation by SOC, PT
- TEAEs leading to cerdulatinib reduction by PT
- TEAEs leading to cerdulatinib reduction by SOC, PT
- Fatal TEAEs by PT
- Fatal TEAEs by SOC, PT.

TEAEs leading to rituximab dose modifications and discontinuations will be listed only.

Summaries (all-grade and grade 3 or above) will be provided for cytopenia category by combining following preferred terms in the AE dataset:

- Neutropenia: neutropenia, neutrophil count decreased, febrile neutropenia
- Thrombocytopenia: thrombocytopenia, platelet count decreased
- Anaemia: anaemia.
- Leukopenia: leukopenia, white blood cell count decreased
- Lymphopenia: lymphopenia, lymphocyte count decreased

For the following categories of TEAEs of special interest, the time to the first onset of the event will be analyzed (e.g. median/mean and min/max).

- All-grade gastrointestinal disorders of special interest
- Grade 3 or higher gastrointestinal disorders of special interest
- All-grade infections of special interest (lower respiratory bacterial infections)
- Grade 3 or higher infections of special interest (lower respiratory bacterial infections)

The relationship between all-grade infections of interest and concomitant compliance use of antimicrobial prophylaxis will be explored. In addition, gastrointestinal disorders and infections of special interest may be analyzed for certain population subgroups as appropriate.

In addition, selected safety summaries will be repeated for the subset of phase 2a subjects with 30 mg BID as starting cerdulatinib dose.

A summary of the number of deaths and the primary cause of death, classified by deaths within 30 days of last dose of study drug and deaths beyond 30 days after the last dose, will be provided.

7.8.1.1. Dose limiting toxicity in Phase 1

The number and percentage of patients experiencing dose limiting toxicities as captured in the eCRF by the investigator during Phase 1 will be summarized by initial dose cohort.

DLT is defined as any of the following toxicities, possibly or probably related to cerdulatinib, and clinically significant (in the judgement of the investigator) that occurs in the first 28 days (one cycle) of treatment. For patients to be evaluable for DLT, they must have received 80% of the doses in the first 28 days of Cycle 1, or been withdrawn from study therapy due to a drug-related toxicity. Patients who withdraw without meeting these criteria should be replaced.

Toxicity will be graded according to the NCI-CTCAE v4.0.

Hematologic

- Febrile neutropenia (ANC < 1,000/ μ L and temperature \geq 38.5°C).

- Grade 4 neutropenia for > 5 days.
- Grade 4 thrombocytopenia with or without bleeding.
- Grade 3 thrombocytopenia with bleeding.
- Grade 4 anemia, unexplained by underlying disease.

Non-hematologic

- Grade 3 or greater nausea, vomiting, or diarrhea if persistent despite optimal antiemetic or anti-diarrheal therapy.

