#### **5.2.1.3. Dose Modifications for Cerdulatinib**

##### **5.2.1.3.1. Dose Modifications to Cerdulatinib During Phase 2a**

Dose reductions and interruptions are permitted during all cycles. Guidelines for dose modifications are provided in [Table 8](#).

In general, for Grade 1 or 2 adverse events that are medically manageable, the Investigator is encouraged to continue dosing and institute standard of care support or hold dosing and institute standard of care support, and then restart dosing at the same dose after the event has resolved to baseline. Specific guidance for management of Grade 1 and 2 diarrhea and nausea and vomiting is provided in [Sections 5.2.1.5](#) and [5.2.1.6](#).

For adverse events  $\geq$  Grade 3, rather than dose interruption or dose reduction, the Investigator is encouraged to hold dosing and institute standard of care support, and then restart dosing at the same dose after the event has resolved to baseline, as clinically appropriate. [Table 8](#) provides further guidance on Grade 3 toxicities. A dose interruption does not necessitate a subsequent dose reduction. In the case of a dose interruption, once the toxicity has resolved to Grade < 2 or

baseline, the Investigator should use clinical judgement when deciding to restart the patient at the same dose level or at a reduced dose.

Patients may be dose-reduced in increments from their starting dose, one level at a time, to the lowest dose level of 15 mg BID. A patient experiencing a toxicity at 15 mg BID should be discontinued from cerdulatinib and removed from the study (after completing the 30 Day Post-Last Treatment Visit in Section 7.3.2.2).

Patients who experience dose interruptions > 28 days in duration should be permanently discontinued from cerdulatinib therapy (after completing the 30 Day Post-Last Treatment Visit in Section 7.3.2.2). Exceptions that would allow such patients to continue study treatment may be allowed at the discretion of the Investigator based upon clinical judgement and with Sponsor Medical Monitor approval.

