**Table 8: Guidelines for Dose Reductions for Cerdulatinib**

Toxicity	Occurrence	Action 
Hematologic Grade 3 or 4 febrile neutropenia Grade 4 neutropenia for $\geq 7$ days, or Grade 4 thrombocytopenia	1 st	Hold study drug. Once toxicity has resolved to Grade < 2 or baseline, may restart cerdulatinib at the next lower dose level.
	2 nd	Hold study drug. Once toxicity has resolved to Grade < 2 or baseline, may restart cerdulatinib at two dose levels below the starting dose.
	3 rd	Discontinue cerdulatinib
Gastrointestinal Grade 3 or 4 nausea, vomiting, or diarrhea if persistent despite optimal antiemetic or antidiarrheal therapy Grade 3 or greater increase in ALT/AST, total bilirubin	1 st	Hold study drug. Once toxicity has resolved to Grade < 2 or baseline, may restart cerdulatinib at the next lower dose level.
	2 nd	Hold study drug. Once toxicity has resolved to Grade < 2 or baseline, may restart cerdulatinib at two dose levels below the starting dose.
	3 rd	Discontinue cerdulatinib
Other Any other related Grade 3 or 4 non-laboratory toxicity Any other related Grade 3 or 4 laboratory toxicity considered clinically significant by the Investigator (e.g., symptomatic) (Do not dose reduce or hold study drug for asymptomatic amylase or lipase elevations  )	1 st	Hold study drug. Once toxicity has resolved to Grade < 2 or baseline, may restart cerdulatinib at the next lower dose level.
	2 nd	Hold study drug. Once toxicity has resolved to Grade < 2 or baseline, may restart cerdulatinib at two dose levels below the starting dose.
	3 rd	Discontinue cerdulatinib

AE = Adverse event; ALT = Alanine aminotransferase; AST = Aspartate aminotransferase

Note: Grading is NCI CTCAE v5.0.

 Do not dose reduce below 15 mg BID. At 15 mg BID, if any toxicity (Grade 3 or greater AE and/or any clinically significant AE) occurs, discontinue cerdulatinib (and rituximab for the combination cohort of cerdulatinib and rituximab) after completing the 30 Day Post-Last Treatment Visit in Section 7.3.2.2.

  $\geq$  Grade 3 asymptomatic elevations in amylase and lipase have been observed in this study without clinical pancreatitis.

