#### **5.2.1.5. Management of Diarrhea**

Grade 1 or 2: The patient may continue receiving study drug. Institute anti-diarrheal treatment (e.g., loperamide [Imodium®] or diphenoxylate/atropine [Lomotil®]) and consider BRAT (bananas, rice, applesauce, and toast) diet. Persistent Grade 2 diarrhea despite optimal therapy may be managed with dose reduction.

Grade ≥ 3: Hold study drug. Once toxicity has resolved to Grade < 2 or baseline, restart cerdulatinib at the same dose level or at the next lower dose level.

Also, if clinically indicated, the patient should be assessed for *C. difficile* infection.

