7.9.1 Treatment Exposure and Compliance

Extent of exposure to study drugs will be summarized descriptively as the number of cycles started, duration of treatment, duration of treatment without full-day dose interruption (defined as full-day with 0 mg dose actually taken), cumulative total dose per subject, actual dose intensity and relative dose intensity.

The number and percentage of subjects with dose reductions, dose interruptions, dose interruptions ≥ 3 days that are not immediately followed by the end of treatment due to disease progression, and drug discontinuation will be tabulated, and the primary reason for dose modifications will be summarized.

The actual dose intensity (mg/day) is defined as the actual cumulative dose (mg) taken based on the total dose per day divided by treatment duration. The relative dose intensity (RDI) is defined as the ratio of actual dose intensity to the planned dose intensity (i.e. the initial assigned dose level in mg/day) in percentage.

Time to first occurrence of dose reduction/interruption due to an AE will be summarized descriptively. In addition, time to treatment failure, defined as time from start of study treatment to discontinuation of study treatment due to any reason, will be summarized.

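### No planned SAP table shows, by preferred term, which TEAEs led to cerdulatinib interruption, although the protocol encourages holding drug for Grade 3 or higher events

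*SAP*

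**What the plan says.** **SAP 7.8.1, Adverse Events** (the number 7.8.1 is used twice in the SAP). Two cerdulatinib actions have their own tables: "TEAEs leading to cerdulatinib discontinuation by PT" and "TEAEs leading to cerdulatinib reduction by PT", each also by SOC and PT. The list then moves to fatal TEAEs. Interruption has no entry. The same list includes all TEAEs, Grade 3 or higher TEAEs, cerdulatinib-related TEAEs and serious TEAEs, whatever action was taken. For rituximab, events leading to dose modification or discontinuation are to be listed only.

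**SAP 7.9.1, Treatment Exposure and Compliance.** This section counts subjects with interruptions, and separately those with interruptions of at least 3 days not directly followed by stopping for progression. It summarizes the main reason for modifications, dose intensity, relative dose intensity, and treatment duration excluding fully missed days. It adds: "Time to first occurrence of dose reduction/interruption due to an AE will be summarized descriptively".

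**Protocol 5.2.1.3.1.** For Grade 3 or higher events the text reads: "rather than dose interruption or dose reduction, the Investigator is encouraged to hold dosing and institute standard of care support". Once the event is back to baseline, treatment is to resume at an unchanged dose where this is clinically suitable. On interruptions the section adds: "A dose interruption does not necessitate a subsequent dose reduction".

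**Other protocol text on restarting.** After a first listed toxicity, Table 8 says the site "may restart cerdulatinib at the next lower dose level". For Grade 3 or higher diarrhea, Section 5.2.1.5 says to "restart cerdulatinib at the same dose level or at the next lower dose level"; Section 5.2.1.6 allows the same choice for nausea and vomiting. Section 5.1.3 speaks of restarting at a lower level.

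**The concern.** A hold followed by a restart at the same dose is a response that the protocol itself encourages, yet it produces neither a reduction nor a discontinuation. A reader of the planned output could learn how many patients were interrupted and how many had diarrhea, but not how many were interrupted because of diarrhea.

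The protocol treats interruption as safety information. Section 7.6 names reasons for interruption among the data that the Study Committee may review. Section 10.2.4.4 makes a treatment interruption one of the grounds for reporting a laboratory result as an adverse event. Section 3.1.2.2.1 says that the accumulated data will feed the choice of dose for registration studies. Knowing which toxicities forced patients off drug for a time is part of that picture. SAP Section 8, which lists departures from the protocol's analyses, does not mention the omission.

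**Working it through.** The plan states no figure to reproduce here, and no sample size, power or error-rate calculation is involved. The check sets the protocol's dose-modification routes against the planned outputs.

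| Route after a TEAE | All-TEAE table (Grade 3+ table if applicable) | Reduction table | Discontinuation table | SAP 7.9.1 exposure summaries |
|---|---|---|---|---|
| Hold, restart at same dose | Yes | No | No | Counted as an interruption |
| Hold, restart at lower dose | Yes | Probably; rule not stated | No | Interruption and reduction |
| Reduction without hold | Yes | Yes | No | Counted as a reduction |
| Permanent stop | Yes | No | Yes | Counted as a discontinuation |

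1. **First row.** The event is counted as having occurred, and the interruption is counted as having happened, but in separate tables. No output is stated to join them by preferred term.

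2. **Does SAP 7.9.1 supply the join?** The time-to-first-event summary pools reductions with interruptions and is not said to be by term. The primary reason is to be summarized, but the SAP does not say at what level of detail. It could be a single adverse-event category or something finer; nothing promises preferred terms.

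3. **Does relative dose intensity show the hold?** Yes, in amount. SAP 7.1.1 defines treatment duration as last dose minus first dose plus 1, so a hold followed by a restart lies inside the denominator. If k full days are held within a 28-day cycle and all other doses are taken at the assigned level, that cycle's contribution is (28 − k)/28 of plan. The figure falls as k rises, but it does not say which event caused the hold.

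4. **Size of the understatement.** Let h be the share of treatment-modifying TEAEs handled by hold and same-dose restart. The reduction and discontinuation tables together then cover 1 − h. The documents give no frequencies of holds, reductions or discontinuations, so h may lie anywhere from 0 to 1. Any coverage figure would only restate the value assumed for h.

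5. **Second row.** Whether such an event counts as an interruption, a reduction or both is not defined. The protocol text adds to the difficulty. Section 5.2.1.3.1 sets a hold apart from an interruption, although withholding drug is an interruption in the ordinary sense and SAP 7.9.1 counts any day with 0 mg taken as one. It also points to the same dose, while Table 8 points to the next lower level.

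**The case against.** The strongest case against is that the safety plan already covers these events from several sides, and much of that case stands.

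- A reader might infer that events managed by a hold vanish from the adverse event tables. They do not. They are counted among all TEAEs and, where they qualify, in the Grade 3 or higher, related and serious tables. Neutropenia has a combined category, and gastrointestinal disorders and lower respiratory bacterial infections have special-interest analyses.
- A reader might infer that a dose kept up only by repeated holds would look well tolerated. SAP 7.9.1 would show otherwise, through interruption counts, dose intensity and time to first AE-driven modification.
- A reader might infer that holds are the most frequent way in which toxicity changes treatment. The documents give no frequencies. The protocol does not point one way either: for manageable Grade 1 or 2 events, continuing on drug is offered alongside a hold, and for Grade 3 or higher events the same-dose restart is qualified and stands beside Table 8.
- A reader might infer that interruption tables would compare 30, 25 and 20 mg BID. The SAP presents Phase 2a safety by cancer type and repeats selected summaries only for patients who started at 30 mg BID, so new tables in that layout would not make the comparison.

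It is also fair to say that this is a descriptive, exploratory study and that no efficacy estimate depends on the missing table. None of this supplies the link between event and interruption. That narrower gap remains.

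**Conclusion.** The point holds in limited form. No planned table identifies, by preferred term, the TEAEs that led to cerdulatinib interruption, although the protocol encourages a response that produces exactly such events. If any event is managed by hold and same-dose restart, the reduction and discontinuation tables alone understate treatment-modifying toxicity, to a degree that cannot be estimated from the documents.

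The conclusion rests on reading the SAP's list of tables as complete and on taking the primary-reason summary as not broken down by preferred term, since the SAP does not say that it is. It needs no assumption about how often holds occur. It is a worthwhile, inexpensive improvement to the safety reporting, not a flaw that undermines the trial's conclusions.

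**What to change.** In SAP 7.8.1, Adverse Events:

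- Add *TEAEs leading to cerdulatinib interruption*, by PT and by SOC and PT.
- Add *TEAEs leading to any cerdulatinib dose modification (interruption, reduction or discontinuation)*, by SOC and PT.
- Name these tables among the summaries repeated for the 30 mg BID starting-dose subset.
- State how a hold followed by a lower-dose restart is classified: as an interruption, a reduction or both.

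Before programming, confirm that the eCRF records the action taken against each adverse event. SAP 7.9.1 presupposes that interruptions can be attributed to an adverse event, but that does not prove that each one is tied to a specific term.

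The sponsor must also reconcile Protocol 5.2.1.3.1, which distinguishes a hold from an interruption and refers to restarting at the same dose, with Table 8, which refers to the next lower level. The classification depends on the answer. No position is taken here on which rule is right.

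The cost is three descriptive tables, their repeats for the subset, and one classification rule. If the eCRF link turns out to be missing, a listing of interruptions with the recorded reason would be the most that could be offered.

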A 45 mg twice daily (BID) dosing cohort was studied, which showed an increase in AUC and minimum and maximal concentrations ( $C_{min}$  and  $C_{max}$ , respectively). The 45 mg BID level roughly doubled the exposure relative to the 40 to 100 mg once daily (QD) average, achieving steady-state  $C_{min}$  and  $C_{max}$  of 1.5 and 1.8  $\mu$ M, respectively. Under this dose regimen, 1 patient with FL achieved a PR, with what appeared to be a rapid (within 1 week) onset of palpable tumor reduction. Another patient with CLL experienced rapid lymphocytosis, whereas a refractory FL patient demonstrated stable disease (SD). The 45 mg BID dose regimen, however, resulted in 2 DLTs: 1 patient experienced pancreatitis within 2 weeks of dosing, and a second patient experienced Grade 3 fatigue. These findings were discussed at regularly scheduled conferences with the Investigator, during which it was determined that this dose regimen was not tolerated. Of note, the 2 patients with DLTs at 45 mg BID did not achieve the highest exposures at this dose level. Thus, we aggregated all data from the escalation portion of the study to date to explore the PK profile.

All AEs of Grade 3 or higher and all SAEs (including 2 fatal SAEs) considered to be related to cerdulatinib reported during the Phase 1 portion of the study in 43 dosed patients are summarized in Table 4 and Table 5, respectively. (Data cutoff is of 25 March 2016; although Phase 1 is closed to enrollment, dosing with cerdulatinib is still ongoing in several patients enrolled under Phase 1 who have been rolled over into the Phase 2a portion of the study.)

**Table 4: Grade  $\geq$  3 Adverse Events Related to Cerdulatinib by MedDRA Preferred Term: Phase 1 Portion (Completed) of Study 13-601 (N=43)**

AEs by MedDRA Preferred Term	Total Number of Patients (N=43)	
	Number (%) of Patients with Grade $\geq$ 3 AE (N=43)	Number (%) of Patients with AE Any Grade (N=43)
Diarrhea	4 (9.3)	27 (46.5)
Nausea	1 (2.3)	11 (25.6)
Abdominal pain	2 (4.7)	8 (18.6)
Pancreatitis	1 (2.3)	1 (2.3)
Fatigue	5 (11.6)	15 (34.9)
Anemia	3 (7)	5 (11.6)
Neutropenia	3 (7)	5 (11.6)
Thrombocytopenia	1 (2.3)	3 (7)
Febrile Neutropenia	1 (2.3)	1 (2.3)
Pancytopenia	1 (2.3)	1 (2.3)
Neutrophil count decreased	2 (4.7)	3 (7)
LDH increased	1 (2.3)	2 (4.7)
AST increased	1 (2.3)	1 (2.3)
Decreased appetite	1 (2.3)	7 (16.3)
Hyponatremia	1 (2.3)	2 (4.7)
Pneumonia	2 (4.7)	2 (4.7)
Lung infection	1 (2.3)	1 (2.3)

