Pneumocystis jirovecii pneumonia a	1 (2.3)	1 (2.3)
Macular rash	1 (2.3)	1 (2.3)
Hypotension	1 (2.3)	2 (4.7)

AE = Adverse event; MedDRA = Medical dictionary for regulatory activities

Note: Data cutoff: 25 March 2016.

a Fatal.

Source: Data on file at Portola (clinical study database). The Phase 1 portion of the study is closed to enrollment; however, some patients enrolled under Phase 1 are still receiving cerdulatinib in Phase 2a.

**Table 5: All Serious Adverse Events Related to Cerdulatinib by MedDRA Preferred Term: Phase 1 Portion (Completed) of Study 13-601 (N=43)**

Serious Adverse Event by MedDRA Preferred Term	Number (%) of Patients (N=43)
Anemia	1 (2)
Blood and Lymphatic System Disorders - Other, specify: Pancytopenia	1 (2)
Diarrhea	1 (2)
Febrile Neutropenia	1 (2)
Fever	1 (2)
Hypotension	1 (2)
Lung infection a	1 (2)
Nausea	1 (2)
Pancreatitis	1 (2)
Pneumonia	1 (2)
Pneumocystis jirovecii pneumonia a	1 (2)

AE = Adverse event; MedDRA = Medical dictionary for regulatory activities

Note: Data cutoff: 25 March 2016.

a Fatal.

Source: Data on file at Portola (clinical study database). The Phase 1 portion of the study is closed to enrollment; however, some patients enrolled under Phase 1 are still receiving cerdulatinib in Phase 2a.

Pharmacokinetic modeling and exploration of the PK/PD and PK/AE data from the Phase 1 portion indicated that a dose of 35 mg BID should provide adequate exposure as well as inhibition of the desired targets of cerdulatinib. Further explanation of the data and rationale for dosing during Phase 2a portion of the study is provided in Section 3.1.2.2.

During Phase 1, PRs have been observed in CLL (including 17p deleted CLL), FL, and transformed follicular lymphoma. CR was observed in 2 FL patients. Responses typically occurred after 2 cycles and have been durable in several patients [18].

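### The combined cytopenia categories omit pancytopenia, so a patient coded only to that term would be missed in four of the five categories

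*SAP*

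**What the plan says.** SAP 7.8.1 (Adverse Events) states: "Summaries (all-grade and grade 3 or above) will be provided for cytopenia category by combining following preferred terms in the AE dataset". Five lists follow. Four of them concern cell lines that pancytopenia would involve:

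- "Neutropenia: neutropenia, neutrophil count decreased, febrile neutropenia"
- "Thrombocytopenia: thrombocytopenia, platelet count decreased"
- "Anaemia: anaemia"
- "Leukopenia: leukopenia, white blood cell count decreased"

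The fifth is lymphopenia. There is no provision for terms outside the lists, and the SAP does not mention pancytopenia anywhere.

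The protocol does. In section 1.5, Table 4 gives pancytopenia a row of its own among related Grade 3 or higher events (1 of 43), and Table 5 lists it among related serious events as "Blood and Lymphatic System Disorders - Other, specify: Pancytopenia".

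Protocol 10.2.4, 10.2.4.1 and 10.2.4.4 tell sites to prefer a unifying diagnosis to separate signs, symptoms or laboratory findings.

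**The concern.** Grouping preferred terms makes a reported rate depend less on which term a site happened to choose. These lists already go beyond plain synonyms, since febrile neutropenia is placed under neutropenia. Pancytopenia denotes low counts in several lines, yet it contributes to no category. If it is a patient's only cytopenia entry, that patient is absent from four summaries at once. An omission of this kind can only lower the rates.

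The laboratory section does not close the gap. SAP 7.8.2 (Laboratory Values) plans descriptive statistics and changes from baseline for selected haematology tests, not the incidence of graded cytopenias. Blood counts also matter for this drug: protocol 7.5.2.1 asks for close monitoring for bone marrow suppression. Protocol 4.1.2, item 7, relaxes the neutrophil and platelet limits for CLL and sets none for certain PTCL subtypes when the cytopenia is due to disease.

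**Working it through.** **Inputs.** Protocol 1.5, Table 4 (related events, N = 43, cutoff 25 March 2016), Grade 3 or higher:

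- pancytopenia 1
- thrombocytopenia 1
- anemia 3
- neutropenia 3, neutrophil count decreased 2, febrile neutropenia 1

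The text introducing Table 4 says it covers all related events of Grade 3 or higher. It has no row for platelet count decreased, leukopenia or white blood cell count decreased, so I take those as 0.

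**Reproducing the documents' figure.** 1/43 = 2.3%, as in Table 4, which rounds to the 2% in Table 5. Table 4 shows only one related pancytopenia patient at any grade, so the serious case in Table 5 is the same patient.

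**Method.** Patient overlap between terms is not reported. A category count therefore lies between its largest single term (complete overlap) and the sum of its terms (no overlap). Adding pancytopenia adds 0 or 1 patient.

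| Category, related Grade ≥3 | SAP list | With pancytopenia |
|---|---|---|
| Thrombocytopenia | 1 (2.3%) | 1 to 2 (2.3% to 4.7%) |
| Anaemia | 3 (7.0%) | 3 to 4 (7.0% to 9.3%) |
| Neutropenia | 3 to 3+2+1 = 6 (7.0% to 14.0%) | 3 to 7 (7.0% to 16.3%) |
| Leukopenia | 0 (0%) | 0 to 1 (0% to 2.3%) |

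**Reading the table.** Each upper end needs two conditions: the patient had no separately coded component term, and the lineage itself reached Grade 3. For leukopenia only the second condition is open, because no related Grade 3 or higher component term was recorded in anyone.

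**Any grade.** Table 4 shows only terms with at least one Grade 3 or higher event, so the any-grade category totals cannot be fully rebuilt. The shift is still at most one patient per category.

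**Precision.** Exact 95% intervals are 0.1% to 12.3% for 1/43 and 0.6% to 15.8% for 2/43. They overlap almost entirely.

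**The case against.** A reader might infer that low counts in all lines are always entered as pancytopenia alone. The documents do not say so. Pancytopenia is not among the examples in protocol 10.2.4.1. The same section asks for separate entries when findings cannot be characterised as one diagnosis, and 10.2.4.2 asks for them when the association is unclear. Whether the Phase 1 patient also had component terms is not shown. The recording text is also the current version, whereas the case predates April 2016, and the amendment summary says the safety section was later revised for clarity. Sole coding is plausible, not established.

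A reader might also say that the thrombocytopenia rate doubles, or that the most severe cases are lost. The first is 1 to at most 2 patients. The second does not follow, because low counts in several lines are not necessarily the most severe, and only one case is documented.

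Three further objections stand:

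- The event is not lost from the report. It appears under its own term in the all-event, Grade 3 or higher, related and serious tables. No endpoint, test or stopping rule uses the combined categories.
- The Phase 1 figures illustrate rather than predict. They cover related events pooled over dose levels. The SAP categories are not limited to related events, Phase 1 is summarised by initial dose level, and no Phase 2a pancytopenia count is given.
- Simply adding the term to every list would create a new error at Grade 3 or higher. A pancytopenia record carries one grade for the whole event, which one lineage may have driven. Crediting that grade to four lineages has no support.

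These points limit the size of the problem and shape the remedy. They do not explain why a term already seen in this trial is missing from the lists.

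**Conclusion.** The gap is real, modest, and worth closing before database lock. As written, the lists can undercount neutropenia, thrombocytopenia, anaemia and leukopenia, and cannot overcount them through this route. The size rests on one Phase 1 patient: at most one extra patient in each of the four categories at related Grade 3 or higher, and possibly none in any of them. The upper figures assume that this patient has no component terms coded separately and reached Grade 3 in the lineage concerned. The Phase 2a effect cannot be estimated from the documents and may be nil. The point concerns the accuracy of a supplementary descriptive summary. It does not mean that the event goes unreported or that any conclusion of the trial changes.

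**What to change.** Before database lock:

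1. In the all-grade summary, add pancytopenia to the neutropenia, thrombocytopenia, anaemia and leukopenia lists, counting each patient once per category.
2. For Grade 3 or higher, choose one rule and state it in the SAP. Either assign the grade by lineage from the haematology values already collected (protocol 7.1.9.1), stating the time window around the event and the CTCAE version, or show pancytopenia as its own row with a sensitivity count that adds it to the four categories.
3. Check the AE dataset for other multi-lineage terms and treat them in the same way.

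The cost is a short SAP change and some programming, more if lineage grades are derived from laboratory data. No new data are needed. The rates may become slightly less favourable.
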